### **9.3.3. Duration of Response**

Duration of response (DR) is defined as the time from the first objective documentation of complete or partial response that is subsequently confirmed to the first documentation of disease progression or to death due to any cause, whichever occurs first. DR will be calculated for the subgroup of patients with objective disease response. DR will be summarized using Kaplan-Meier methods and displayed graphically where appropriate. The median event time and 2-sided 95% CI for the median will be provided if appropriate. The number of patients experiencing CR and PR may be small and thereby limit the use of the Kaplan-Meier method to provide reliable information. In this case, descriptive statistics or listings will be provided.

### **9.3.4. Overall Survival**

Overall survival (OS) is defined as the time from enrollment to the date of death due to any cause. OS data will be censored on the day following the date of the last contact at which the patient is known to be alive. OS will be summarized using Kaplan-Meier methods and displayed graphically where appropriate. The median survival time and 2-sided 95% CI for the median will be estimated.

The 2-year survival probability will be estimated using the Kaplan-Meier method and a 2-sided 95% CI for the log [-log(1-year survival probability)] will be calculated using a normal approximation and then back transformed to give a CI for the 2-year survival probability.

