#### **Secondary Endpoints:**

- Type, incidence, severity (graded by the National Cancer Institute (NCI) Common Terminology Criteria for Adverse Events [CTCAE], Version 4.0 [v4.0]), timing, seriousness, and relatedness of adverse events and laboratory abnormalities;
- Objective response rate, duration of response, PFS and OS at 2 years after study enrollment;
- Pharmacokinetic-pharmacodynamic relationships with respect to safety and efficacy in pediatric GIST, if data allows.

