##### **7.4.1. Time-To Event Endpoints**

For the purposes of endpoint definitions, the term “on-study” includes the period of study medication treatment plus 28 days following the last dose of study medication.

Progression-free survival (PFS) is defined as the time from the date of enrollment to the date of the first documentation of objective tumor progression.

PFS will be censored on the date of the last on-study tumor assessment documenting absence of progressive disease for patients who are alive, on study and progression free at the time of the analysis, are given antitumor treatment other than study treatment or are removed from treatment prior to documentation of disease progression or death on study. For PFS, patients having no tumor assessments after screening will have tumor related endpoints censored on the date of enrollment. Other censoring situations will be described in detail in the statistical analysis plan (SAP), for each endpoint analyzed.

Overall Survival (OS) is defined as the time from the date of enrollment to the date of death due to any cause. For patients still alive at the time of analysis, the OS time will be censored on the last date the patients were known to be alive. Patients lacking data beyond enrollment will have their OS censored at date of enrollment.

The 2-year survival probability is defined as the probability of survival at 2 years after the date of enrollment based on the Kaplan-Meier estimate.

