### 2. INTRODUCTION

This document describes the planned statistical analyses for Protocol A6181196 dated 17 June 2011. This analysis plan is meant to supplement the study protocol. Any deviations from this analysis plan will be described in the Clinical Study Report.

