## **9. STATISTICAL METHODOLOGY AND STATISTICAL ANALYSES**

Statistical analysis and data presentation will be performed on the subgroups of patients aged 6 years to less than 18 years, and patients aged 18 years to less than 21 years, respectively. A pooled data analysis including all the patients enrolled in the study will also be performed. Also, analysis of time-to-event efficacy endpoints will be performed only if sufficient number of events permit meaningful estimates.

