#### **9.1.2. Analysis of Efficacy Endpoints**

##### **9.1.2.1. Objective Response Rate**

Objective response rate (ORR) is defined as the proportion of patients with a confirmed complete (CR) or partial response (PR) relative to the number of patients in the treatment group according to RECIST criteria (Version 1.1). The number and percent of patients achieving objective response (CR or PR) will be summarized along with the corresponding exact 2-sided 95% CI calculated using a method based on the F distribution.

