### **9.1.2.4. Overall Survival**

Overall survival (OS) is defined as the time from enrollment to the date of death due to any cause. OS data will be censored on the day following the date of the last contact at which the patient is known to be alive. OS will be summarized using Kaplan-Meier methods and displayed graphically where appropriate. The median survival time and 2-sided 95% CI for the median will be estimated.

The 2-year survival probability will be estimated using the Kaplan-Meier method and a 2-sided 95% CI will be constructed for the 2-year survival probability.

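### The Protocol's confidence interval for 2-year survival is built on the 1-year survival probability

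*Protocol*

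**What the plan says.** Protocol 2.2 lists among the secondary endpoints "Objective response rate, duration of response, PFS and OS at 2 years after study enrollment", and SAP 6.2 repeats it. Protocol 7.4.1 fixes the time point: "The 2-year survival probability is defined as the probability of survival at 2 years after the date of enrollment", taken from the Kaplan-Meier curve. Neither document defines a 1-year survival endpoint.

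Protocol 9.3.4 estimates 2-year survival by Kaplan-Meier and then gives the interval rule: "a 2-sided 95% CI for the log [-log(1-year survival probability)] will be calculated using a normal approximation", "then back transformed to give a CI for the 2-year survival probability".

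SAP 9.1.2.4 says only that "a 2-sided 95% CI will be constructed for the 2-year survival probability". It names no transform and no variance estimator. Elsewhere the SAP does name an interval method: for the response rate it specifies an "exact 2-sided 95% CI calculated using a method based on the F distribution". That is a different quantity and does not fill the gap. SAP section 2 states the relation between the documents: "This analysis plan is meant to supplement the study protocol".

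**The concern.** The sentence in Protocol 9.3.4 holds two time points. The estimate and the label are at 2 years, while the quantity inside the transform is at 1 year. Back-transforming only undoes log(-log); it cannot carry an interval from year 1 to year 2.

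A programmer who follows the sentence would print the 2-year estimate beside the 1-year interval. Survival cannot rise between the two dates, so the error runs one way: whenever deaths occur in both years, the printed interval is too favourable, and it may not contain the estimate it accompanies. If the first year is free of deaths, the rule breaks down although a valid 2-year interval may exist. A death-free first year is plausible here, since Protocol 1.1 describes paediatric GIST as indolent, with most patients surviving for many years.

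**Working it through.** The plan gives no figure to reproduce. The check is to evaluate the written rule and the intended rule on the same data.

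**Inputs**
- Two-sided 95% interval, normal approximation on log(-log S): Protocol 9.3.4. The normal quantile is z = 1.96.
- n = 6 children: Protocol sections 3 and 9.1.
- n = 21, that is 6 + 15, the permitted maximum with young adults (Protocol section 3). This is not an expected size.
- Assumptions: the death counts below are illustrative, there is no censoring before 2 years, and the variance is Greenwood's, since neither document names one.

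**Formulas**

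With d deaths by time t and no censoring:
- S = (n − d)/n
- Greenwood sum g = d/[n(n − d)]
- θ = log(−log S), with SE = √g / |log S|
- limits = exp(−exp(θ ± 1.96·SE))

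The written rule uses d at 1 year. The intended rule uses d at 2 years.

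**One case in full: n = 6, 1 death in year 1, 3 deaths by year 2**
- 1 year: S = 5/6 = 0.833; g = 1/(6·5) = 0.0333; θ = −1.702; SE = 1.001; limits 0.273 and 0.975.
- 2 years: S = 3/6 = 0.500; g = 3/(6·3) = 0.1667; θ = −0.367; SE = 0.589; limits 0.111 and 0.804.

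**Cases side by side**

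| n | Deaths by year 1, by year 2 | 2-year estimate | Interval as written | 2-year interval |
|---|---|---|---|---|
| 6 | 1, 1 | 83.3% | 27% to 97% | 27% to 97% |
| 6 | 1, 2 | 66.7% | 27% to 97% | 19% to 90% |
| 6 | 1, 3 | 50.0% | 27% to 97% | 11% to 80% |
| 6 | 0, 1 | 83.3% | none | 27% to 97% |
| 21 | 2, 6 | 71.4% | 67.0% to 97.5% | 47.2% to 86.0% |
| 21 | 2, 7 | 66.7% | 67.0% to 97.5% | 42.5% to 82.5% |
| 21 | 0, 1 | 95.2% | none | 71% to 99% |

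The entry is none where S(1 year) = 1, because log[−log(1)] is undefined. In the 2, 7 row the written interval starts just above its own estimate.

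**All patterns**

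Take every pair with at least 1 death by year 1, more deaths by year 2, and at least 1 survivor.
- n = 6: 10 pairs. Both limits are too high in all 10. The estimate is excluded in 2 (1 then 5 deaths, and 2 then 5).
- n = 21: 190 pairs. Both limits are too high in all 190. The estimate is excluded in 118.

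These are counts of patterns, not probabilities, and many of them involve heavy mortality. At n = 21, exclusion occurs in 0 of 15 patterns with at most 6 deaths by year 2, in 5 of 28 with at most 8, and in 12 of 45 with at most 10.

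**The case against.** The strongest reply is that the slip corrects itself. The same Protocol sentence says 2 years before and after the error, every endpoint definition says 2 years, and Protocol section 9 leaves the detailed methodology to the SAP and lets it modify the Protocol's plans. A programmer working from the SAP has the right time point. That stands, and it is why the point is minor. It does not close the matter, because the SAP supplies no formula to replace the faulty one. Nor is its wording clearly a deliberate correction: it was written for a protocol dated 17 June 2011 and still plans 15 children.

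A second reply is that SAP section 9 says "analysis of time-to-event efficacy endpoints will be performed only if sufficient number of events permit meaningful estimates". With 1 to 3 deaths among 6 children, the interval might never be produced. This is fair, but no threshold is given, so the rule weakens the small-sample examples without removing them.

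A third is that exclusion of the estimate needs high mortality: at least 7 deaths by year 2 at n = 21, or 5 of the 6 children. That is correct, and exclusion should not be read as the expected outcome. The upward shift of both limits needs no such extreme. It appears with 1 death in each year.

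**Conclusion.** The concern holds. As written, Protocol 9.3.4 produces a 1-year interval under a 2-year label, and no other text in the two documents states how the interval is to be computed.

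The size depends on when deaths occur. Without censoring, nothing changes if there are deaths in year 1 and none in year 2. With deaths in both years, both limits are too high; in the illustrations for 6 children the lower limit is overstated by about 8 to 16 percentage points (27% against 19% and 11%). With the first death in year 2, the interval is missing. These figures rest on assumed death counts, complete follow-up to 2 years and Greenwood's variance.

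The endpoint is secondary and descriptive and no decision rule depends on it, so the effect is confined to how 2-year survival is reported. Severity is minor; confidence in the finding is high.

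**What to change.** In Protocol 9.3.4, change 1-year to 2-year inside the transform.

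In SAP 9.1.2.4, add one sentence naming the method, for example: *The 95% CI is the normal-approximation interval for log[−log S(2 years)], using Greenwood's variance, back-transformed.*

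Optionally, add that when the 2-year Kaplan-Meier estimate is 1 or 0 it is reported without this interval and survival times are listed. The corrected formula is undefined there too, and SAP 9.1.2.3 already takes this approach for duration of response. The event-number rule in SAP section 9 is unaffected.

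The cost is one word and one sentence, with no new data, endpoint or analysis. A protocol edit needs ethics committee approval (Protocol 12.1), so it is best carried with the next amendment. Protocol section 9 requires an amendment only for major changes to the primary endpoint or its analysis, so the SAP sentence can settle the rule in the meantime.

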### Document History

Document	Version Date	Summary of Changes and rationale
Amendment 1	11 June 2012	
The Schedule of Activities and associated protocol sections were revised to include growth and pubertal maturation assessments for paediatric patients, a reduced mandatory visit schedule after Cycle 3, and clarification of standard tumor analysis requirements.
 
The term “chemotherapy naïve” was removed from the study design and the associated secondary objective to study tolerability in pediatric patients with GIST.
 
Multiple changes were made according the new Pfizer standard safety language for clinical protocols. One significant change in safety language is the following in Section 8.2 Reporting Period: Should an investigator be made aware of any SAE occurring any time after the active reporting period, it must be promptly reported. Previously, this SAE reporting required a potential causal relationship to the study drug.
 
A change in contraception language for the UK was made at the request of the

		
UK regulatory authorities.
 
Administrative changes and clarifications made throughout.

Amendment 2	31 July 2017	
The number of patients to be enrolled in the study (in the range of age from 6 to < 18) has been reduced from 15 to 6 evaluable patients.
 
The centralized review of imaging (ie, MRI, CT scans etc) aimed to confirm the efficacy endpoint is no longer required.
 
As this study is part of a PIP, both these changes above have been agreed with PDCO and are aligned with the PIP binding elements.
 
Rationale for changes are as follow:
 
The primary objective of the study is the characterization of plasma PK profile of sunitinib and its active metabolite in patients with unresectable GIST. A total of six pediatric patients have been included in the study as of today, and the enrollment of additional patient is unlikely due to the rarity of the disease. Recognizing this number is lower than originally planned it still allows the characterization of the pk profile in pediatric patients i.e the analysis of the primary endpoints of the

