## 1. INTRODUCTION

### 1.1. Indication

#### Pediatric GIST

Gastrointestinal stromal tumor (GIST) is a tumor of mesenchymal origin occurring in the gastrointestinal tract. GIST is a very rare and newly recognized tumor in children. Pediatric GIST has a different clinical behavior and biology than typical adult GIST. In contrast to GIST in adults, the vast majority of pediatric GIST occur in females, lack large scale chromosomal aberrations, and lack the characteristic mutations in *KIT* or *PDGFRA*. Despite multiple recurrences and lack of dramatic responses to tyrosine kinase inhibitor therapy, most pediatric patients survive with active disease for many years, suggesting a more indolent clinical course than observed with adult GIST. Further evidence supporting a distinct biology comes from recently published reports of differing gene-expression profiles and genetic progression mechanisms in pediatric GIST versus adult GIST. While most pediatric GIST lack *KIT* mutations, *KIT* is expressed and activated, suggesting that inhibition of *KIT* may have clinical efficacy in these tumors. *In vitro* data show that sunitinib's IC50 is 90% lower than imatinib's IC50 for mutation-negative *KIT*. Early clinical studies seem to correspond with the *in vitro* data. Clinical benefit rate (defined as partial response [PR] or stable disease [SD] in *KIT* mutation-negative GIST is 56% versus 34% in adult, *KIT* mutation-positive GIST. Median OS was also significantly longer for adult patients with exon 9 *KIT* mutations (26.9 months) or a mutation-negative genotype (30.5 months) than for those with exon 11 mutations (12.3 months). Neither PFS nor OS differed significantly between patients with exon 9 *KIT* mutations or a mutation-negative genotype. Currently there is no evidence to suggest that pediatric mutation-negative GIST would differ biologically or clinically from adult mutation-negative GIST. A recent study suggests that a proportion of *KIT* mutation-negative GIST tumors have mutations in succinate dehydrogenase (*SDH*). Such mutations result in a loss of SDH expression in these tumors that can be assessed by immunohistochemistry. A loss in SDH expression could potentially result in increases in intra-tumor VEGF expression. Antitumor activity has been reported with sunitinib, which targets the VEGF signaling pathway, in a cohort of pediatric patients with imatinib-resistant, predominantly *KIT* mutation-negative GIST. One of seven of these patients achieved PR, five patients had SD and one patient had PD on sunitinib. In most pediatric patients treated with imatinib followed by sunitinib, the time to progression on sunitinib was longer than on prior imatinib.

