### **3. STUDY DESIGN**

This study is a single arm, multi-center, multi-national, clinical trial evaluating the PK, safety and preliminary anti-tumor efficacy of sunitinib in children and young adults diagnosed with advanced, unresectable GIST. The study aims to enroll 6 evaluable patients aged 6 years to less than 18 years. In addition, up to 15 young adults aged 18 - <21 years diagnosed with GIST may be enrolled.

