## **9.1. Sample Size Determination**

Due to the rarity of the disease and the difficulties in identifying pediatric patient suitable for participation in this study only 6 patients will be included. The statistical power has not been calculated. Descriptive analysis approach will be adopted to report study results.

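### The planned log(-log) interval for 2-year survival does not exist if nobody dies, a plausible result in 6 children, and neither document names a replacement

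*Protocol*

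**What the plan says.** Overall survival at 2 years after enrollment is a secondary endpoint (Protocol 2.2, SAP 6.2).

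- **Protocol 9.3.4** estimates 2-year survival by Kaplan-Meier. It forms "a 2-sided 95% CI for the log [-log(1-year survival probability", which "will be calculated using a normal approximation and then back transformed to give a CI for the 2-year survival probability". There is no rule for the case without deaths.
- **SAP 9.1.2.4** says only that "a 2-sided 95% CI will be constructed for the 2-year survival probability". It names neither log(-log) nor any other method.
- **SAP section 9** adds a condition: "analysis of time-to-event efficacy endpoints will be performed only if sufficient number of events permit meaningful estimates". It gives no number of events and does not say what is reported otherwise. It also commits to separate analyses of the two age groups and a pooled analysis. Protocol 9.3 makes the age subgroups optional.
- **Numbers.** Protocol 9.1 says that "only 6 patients will be included" on the pediatric side. Protocol section 3 adds that "up to 15 young adults aged 18 - <21 years diagnosed with GIST may be enrolled", so the full analysis population is 6 to 21. The Document History says of the six children that "the enrollment of additional patient is unlikely due to the rarity of the disease". The number of young adults enrolled is not given.
- **Prognosis.** Protocol 1.1 says that "most pediatric patients survive with active disease for many years". It gives no 2-year survival rate for children.

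**The concern.** The log(-log) interval needs at least one death. In a group of 6 with a disease described as indolent, all patients being alive at 2 years is a result that the plan should be able to handle. As written, the prescribed formula then gives nothing, and what to report would be decided after the data are seen.

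The interval matters most in that case. A report of 6 of 6 alive reads as 100% survival, and only a lower confidence limit tells the reader how little 6 patients can establish.

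The mention of 1-year survival inside an expression meant for 2 years is a separate slip in the same sentence. This point does not depend on it.

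**Working it through.** The documents state no expected survival, number of deaths or precision for overall survival, so there is no figure of theirs to reproduce. The check computes the planned interval directly. It assumes that every patient is followed to death or 2 years.

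**1. The planned interval.** With n patients and d deaths by 2 years:
- S = 1 − d/n
- Greenwood sum = d / [n(n − d)]
- se of log(−log S) = √(Greenwood sum) / |log S|
- limits = S^exp(±1.96 × se)

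*Zero deaths:* S = 1, so −log S = 0 and log(−log S) is minus infinity. The Greenwood sum is 0 and the se is 0/0. No interval exists at any n.

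*One death in 6:* S = 0.833, Greenwood sum = 1/30, se = 0.1826/0.1823 = 1.001. The limits are 27.3% and 97.5%. The formula works here; the exact (Clopper-Pearson) interval is 35.9% to 99.6%.

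**2. How often zero deaths occurs.** P(no deaths) = S^n. The survival rates in the first four rows are assumptions. The last row uses the adult mutation-negative median of 30.5 months (Protocol 1.1) with exponential survival: S = 0.5^(24/30.5) = 0.58.

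| True 2-year survival | n = 6 | n = 21 |
|---|---|---|
| 80% | 26% | 1% |
| 90% | 53% | 11% |
| 95% | 74% | 34% |
| 98% | 89% | 65% |
| 58% (adult median) | 4% | about 0% |

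For n = 6, zero deaths is more likely than not only if S is at least 0.5^(1/6) = 89.1%. For n = 21 the corresponding value is 0.5^(1/21) = 96.8%.

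**3. What an exact interval gives.** With zero deaths the lower 95% limit is 0.025^(1/n):
- n = 6: 54.1% to 100%
- n = 21: 83.9% to 100%

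**4. Coverage at n = 6.** When the log(-log) interval exists, it covers the true value with probability 98%, 97% and 88% at true survival of 80%, 90% and 95%. The minimum coverage of the exact interval over all true survival values is 96.6%, reached near 54%.

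**5. Whether another passage fills the gap.** For duration of response, Protocol 9.3.3 and SAP 9.1.2.3 give a sparse-data fallback of descriptive statistics or listings. The overall survival sections have none. For response rate, Protocol 9.3.1 requires an exact 95% CI, and SAP 9.1.2.1 specifies the F-distribution method, which is Clopper-Pearson. The sponsor thus already uses an exact interval for a proportion in these patients, but not for this one.

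**The case against.** **The SAP already stops the analysis.** Zero deaths is the clearest case of too few events, so the condition in SAP section 9 would probably prevent the calculation. A reader might infer that the report will show 100% with a degenerate interval from 100% to 100%. The documents do not lead there. But the condition has no threshold and no alternative output, so applying it leaves the endpoint with no interval.

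**The SAP does not prescribe log(-log).** This is correct: an exact interval would comply with SAP 9.1.2.4, and Protocol section 9 lets the SAP modify the protocol's plans. However, the SAP describes itself as a supplement to the protocol and names no substitute, so the protocol's formula is the only method on paper.

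**Zero deaths may be unlikely.** A reader might infer from the indolent course that it is the expected result. The documents do not support that. The text is general background, no pediatric rate is given, and Protocol 1.1 also says there is no evidence that pediatric mutation-negative disease differs clinically from the adult form, whose median implies about 4%. The same section calls pediatric GIST more indolent than adult GIST. Plausible is as far as the evidence goes.

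**Six is not the main efficacy set.** Efficacy is analysed in all enrolled patients, possibly 21, where zero deaths is much rarer. This stands for the pooled analysis, but the SAP also plans the pediatric subgroup.

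**The method may look poor in general.** Counting a missing interval as a miss, coverage at n = 6 is 72%, 45% and 23% at 80%, 90% and 95% survival. Those figures mostly restate the chance of no deaths. They are not separate evidence against log(-log), as step 4 shows.

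**The impact is limited.** Overall survival is a descriptive secondary endpoint in a PK-primary study without a power calculation, and no decision depends on this interval. This stands.

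**Conclusion.** The gap is real and narrow. The only interval method that either document names for 2-year survival is undefined when nobody dies. The SAP's condition on events does not close the gap, because it has no threshold and no fallback. In the 6-child subgroup the chance of this is 26% to 74% for assumed true survival of 80% to 95%, and about 4% under the adult median. In 21 pooled patients it is 11% at 90% and 34% at 95%. If it happens, readers would not see that 6 of 6 alive is compatible with true survival as low as 54%.

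The probabilities rest on assumed survival rates and independent patients, and the exact limits on complete 2-year follow-up. That the formula fails with zero deaths rests on none of these.

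**What to change.** - **Protocol 9.3.4:** replace the log(-log) interval with the beta product confidence procedure for the Kaplan-Meier estimate, or at minimum prescribe that procedure for the zero-death case. It is defined with no deaths, allows for censoring, and equals Clopper-Pearson when nobody is censored before 2 years, so one rule covers both situations.
- **SAP 9.1.2.4:** name the same method. Nothing has to be removed there.
- **SAP section 9:** state that the 2-year survival estimate and its exact interval are reported even with few or no deaths, by age group and pooled. Define what counts as a sufficient number of events for the other time-to-event analyses.

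The cost is about one sentence in each place. The downside is that the exact interval is conservative: at n = 6 without censoring its coverage is at least about 96.6% against the nominal 95%.
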